3.7 Post-progression therapy

Regardless of initial treatment, patients will have two options for post-progression therapy following BICR-confirmation of PD:

- 1 Receive subsequent non-study anti-cancer therapy that does not contravene local practice.
- 2 Continue to receive the assigned study treatment as long as in the opinion of the investigator, the patient is deriving benefit, and the patient meets the original eligibility criteria in terms of performance status and laboratory values. This decision must be discussed with and approved by the AstraZeneca study physician. Such patients will continue to undergo monitoring as per the Study Plan (Table 1) while on study treatment.

There will be no cross-over.

3.8 Discontinuation of investigational product

Patients may be discontinued from savolitinib or sunitinib in the following situations:

- Patient decision. The patient is at any time free to discontinue treatment, without prejudice to further treatment.
- Adverse Event as per study criteria.
- Pregnancy.
- Severe non-compliance with the Clinical Study Protocol.
- BICR-confirmed PD unless the physician feels that the patient is still deriving benefit from the initial treatment and confirms that the patient meets the original eligibility criteria in terms of performance status and laboratory values. This must be discussed with and approved by the AstraZeneca study physician.
- Patients was incorrectly initiated on investigational product (Section 3.4).
- The investigator decides the patient should not be continued on the trial/is no longer deriving benefit from the study medication.

After discontinuation of the study treatment at any point in the study, all ongoing AEs or SAEs must be followed until resolution or until the event becomes stable (or returns to baseline) unless, in the investigator's opinion the condition is unlikely to resolve due to the patients underlying disease, or the patient is lost to follow up (see Section 6.3.2). All new AEs and SAEs occurring during the 30 calendar days after the last dose of study treatment must be reported (if SAEs, they must be reported to AstraZeneca within 24 hours as described in Section 6.4) and followed to resolution or until the event becomes stable (or returns to baseline) or is unlikely to resolve further in the opinion of the investigator. Patients should be contacted or seen 30 days (± 7 days) after discontinuing the last dose of study medication to collect and /or complete AE information. Any untoward event occurring subsequent to the 30-day follow-up AE reporting period that the investigator assesses as possibly related to the study medication should also be reported as an AE.

AstraZeneca retains the right to request additional information for any patient with ongoing AE(s)/SAE(s) at the end of the study, if judged necessary.

Any patient who has not yet shown BICR-confirmed PD at discontinuation of study medication should continue to be followed with centrally reviewed scans until there is BICR-confirmation of PD, regardless of whether subsequent anti-cancer therapy is started.

3.8.1 Procedures for discontinuation of a patient from study treatment prior to BICR-confirmed PD

Patients who discontinue study-medication prior to BICR-confirmed PD will be asked about the reason(s) for discontinuation and the presence of any AEs. In addition, the date of discontinuation, the reason and any medications taken at the time of discontinuation will be recorded on the eCRF. If a patient discontinues study treatment, the study monitor must be informed immediately.

If the reason for study medication discontinuation is due to investigator-assessment of PD using RECIST 1.1 (but prior to BICR confirmation due to delay or a BICR discrepancy), patients should be encouraged, if not medically contraindicated, to not start subsequent anti-cancer therapy and continue to undergo disease assessments until BICR-confirmed PD. Once there is BICR-confirmed PD, patients will be followed for PFS2 and OS as per Sections 4.3.3 and 4.3.4.

However, if this is not an option for the patient and/or physician, or if the study medication was discontinued for any other reason other than PD, then an EOT visit will be conducted as soon as possible and preferably within 7 days following the decision to discontinue study medication.

The purpose of this visit for patients who discontinue study-drug prior to BICR-confirmed PD is to:

- (a) discuss any additional treatment options and follow-up.
- (b) discuss the possibility of a biopsy, which should be strongly encouraged, particularly for patients who had responded to treatment (patients may have signed a consent line for this on the Main Study ICF).
- (c) obtain the required EOT tests (Table 1) and collect the ePRO device after the last set of questionnaires are completed.
- (d) collect any unused study medication and study-medication containers from the patient.

By discontinuing study treatment, the patient is not withdrawn from the study. If a patient decides to voluntarily withdraw (ie, patient choice), then the Withdrawal ICF (Informed Consent Form Addendum – Options for Withdrawal of Consent) should be used to determine

if they are willing to undergo follow-up. Section 3.9.2 outlines the criteria for withdrawal from study.

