Once a patient permanently discontinues study drug, a 30-day (± 7 days) safety follow-up will be performed to follow-up on any SAE/AEs and concomitant medications (including any subsequent cancer therapy). If there are no ongoing SAE/AEs at the time of drug discontinuation, the safety follow-up can be done via telephone contact.

Determination of PD on subsequent anti-cancer therapy in patients who had PD by RECIST 1.1 on study medication (PFS2) will be by institutional call. Patients who choose to continue on their initial therapy after BICR-confirmed PD will not be considered to have a second PFS event until they discontinue study medication and progress on subsequent anti-cancer treatment.

In the OS follow-up period following second progression (PFS2), subsequent therapies and vital status will be documented at least every 12 weeks until death, lost to follow-up, withdrawal of consent, or end of study, whichever comes first.

A recent review of the final results of the Molecular Epidemiology Study (MES) concluded that in this data-set, [REDACTED]

[figure not shown]
[REDACTED] It was also concluded that the SAVOIR study design would not benefit from a study size reassessment [REDACTED]

Following a review of the MES results, a decision, endorsed by the Independent Data Monitoring Committee (IDMC), was made to terminate recruitment into SAVOIR.

Patients randomised in SAVOIR may continue to receive their assigned treatment for as long as they are deriving clinical benefit or until they meet a protocol-defined stopping criterion and must follow the study plan as outlined. Patients already in screening (who have signed the ICF) will have the option to continue screening and to be randomised if eligible.

Further information can be found in Section 4.3.5.

Figure 1 Study flowchart

BICR, Blinded Independent Central Review; *FH/VHL*, fumarate Hydratase/von Hippel-Lindau; PD, progression of disease; PFS2, second progression-free survival; PO, orally; PRCC, papillary cell renal carcinoma; QD, once a day.

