be performed. The ePRO device and all unused study medication and study medication bottles should be returned.
- 19 A safety follow-up will be performed 30 (± 7) days after discontinuation of study medication, to follow-up on any SAE/AE's and record any subsequent
cancer therapy. If there are no ongoing SAE/AEs at the time of drug discontinuation, the safety follow-up can be done via telephone contact.
- 20 All subsequent anti-cancer therapies and OS status will be documented at least every 12 weeks until death, loss to follow-up, withdrawal of consent, or end
of study, whichever comes first.
- 21 Blood liver functions (AST, ALT, alkaline phosphatase and total bilirubin) will be monitored weekly x 9 and then at the start of each cycle. In some
situations, blood for LFTs may be drawn at a local lab on the days when there is no scheduled clinic visit although the results must be faxed to the treating
institution immediately so they can be evaluated in light of the hepatotoxicity algorithm (Section 6.8.1.2 for savolitinib and Section 6.8.2 for sunitinib) and
entered into the database.
- 22 An IVRS/IWRS transaction needs to be done at every dispensing visit at the start of each cycle. Additionally, every dose reduction needs to be recorded in
IVRS/IWRS.
- 23 Please see section 6.3. From the part 1 screening visit until the part 2 screening visit, only SAEs related to study procedures must be reported (AEs do not
require reporting). From the main study screening (Part 2) onwards, all AEs/SAEs must be reported
- 24 Smoking status (Yes (current smoker) /No (not currently smoking)) will be recorded at the time of the main study screening (Part 2) visit.
- 25 Body weight will be assessed every cycle, and more frequently if clinically indicated. The dose of savolitinib will not change for patients who started the
study at < 50 kg (ie, 400 mg), even if their weight increases to ≥ 50 kg during the course of the study.
- 26 20 mL for [REDACTED] at the Part 1 screening visit only (see Section 5.7.4)
- 27 Only necessary if there are ongoing toxicities
- 28 A tumour biopsy after treatment discontinuation should be strongly encouraged regardless of treatment arm, particularly for patients who had responded to
treatment. See section 5.7.7.
- 29 See Table 2 (Section 5.2.1) for list of chemistry evaluations
- 30 Hepatitis serology includes HBsAg, anti-HBc (qualitative), HBV DNA, HCV antibody, HCV RNA (if HCV antibody is positive)

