7.2.2 Sunitinib

Sunitinib: two 25 mg capsules PO QD, with or without food will be administered in 6-week treatment cycles: 4 weeks on/2 weeks off.

The time of day for administration of sunitinib should be consistent and the actual time the dose is taken should be recorded in the eDiary each day.

If the patient misses a dose of study medication, it should be taken as soon as it is remembered. A missed dose should not be taken, though, if it is close to the next dose. In this case, the next dose should be taken at the regular time. More than 1 dose of sunitinib should not be taken at a time.

If vomiting occurs after taking sunitinib, the patient should be instructed not to retake the dose. Patients should take the next scheduled dose of sunitinib. If vomiting persists, the patient should contact the investigator. Ondansetron or another serotonin-receptor antagonist may be used.

On clinic visit days the patient should be instructed to wait until he/she arrives at the study centre to take their study medication when instructed.

Patients should be advised to bring any unused sunitinib in the original blister packs, in addition to returning any empty blister packs to each clinic visit. Sunitinib dosing compliance

should be reviewed with the patient at each clinic visit, including the visit at the beginning of each cycle when study medication is dispensed.

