- Any AE occurring within the defined 30 day follow up period after discontinuation of investigational product will be included in the AE summaries.
- Deaths will be summarised by primary cause, along with AEs with an outcome of “fatal”.
- Haematology, clinical chemistry, vital signs, ECG, ECHO/MUGA data and concomitant medication will be summarised.
- Any qualitative safety assessments for urinalysis will be presented as is deemed appropriate. This may include, but is not restricted to, presentation of parameters against time, concentration, or shift plots. Appropriate scatter plots will also be considered to investigate trends in parameters compared with baseline.

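### The post-treatment safety contact may fall on day 23 although AE reporting runs to day 30, and the 30-day window starts at the last dose in some clauses and at discontinuation in others

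*Protocol*

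**What the plan says.** **Reporting duty.** Section 3.8: "All new AEs and SAEs occurring during the 30 calendar days after the last dose of study treatment must be reported".

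**Contact.** The following text in 3.8: "Patients should be contacted or seen 30 days", give or take 7 days, to gather and complete AE information. Sections 1.4 and 4.3.2 and footnote 19 of Table 1 repeat the 30 ± 7 day timing. They allow a telephone call if no AE is ongoing when the drug is stopped.

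**After the final analysis.** Section 4.3.5 puts the ± 7 days on the collection period itself for SAEs, overdose and pregnancy, not only on a visit.

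**Start of the clock.**
- Last dose, or last study treatment: 3.8 (reporting duty), and the follow-up of events in 4.3.2 and 6.3.2.
- Discontinuation: 1.4 ("Once a patient permanently discontinues study drug, a 30-day" follow-up), the contact in 4.3.2, 4.3.5, Table 1 footnote 19 ("days after discontinuation of study medication, to follow-up on any" AEs), and the AE summary rule in 8.4.2 ("Any AE occurring within the defined 30 day follow up period after discontinuation of investigational product").
- No anchor: 6.3.1, the section that sets the AE collection period.

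The contact sentence in 3.8 blends the two terms ("Patients should be contacted or seen 30 days (± 7 days) after discontinuing the last dose of study medication"), and 4.3.2 uses both. No clause says that the two dates are the same.

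**Dosing.** Sunitinib "will be administered in 6-week treatment cycles: 4 weeks on/2 weeks off"; savolitinib is continuous.

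**The concern.** A contact meant to collect events up to day 30 should not be allowed to close before day 30. If it takes place on day 23, no later visit or call has AE collection as its stated purpose. Follow-up for second progression and survival is specified for progression, later therapy and vital status.

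The anchor matters because the reporting rule and the summary rule use different clocks. When discontinuation comes after the last dose, 8.4.2 counts any AE up to 30 days after discontinuation. Beyond day 30 from the last dose, 3.8 asks only for this: "Any untoward event occurring subsequent to the 30-day follow-up AE reporting period that the investigator assesses as possibly related to the study medication". The summaries could then include a stretch in which only events judged possibly related had to be reported.

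Safety relative to sunitinib is a stated objective. With about 50 patients randomised 1:1, there are about 25 per arm, so one patient is 1/25 = 4 percentage points in an AE rate.

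**Working it through.** The protocol gives no figure to reproduce; this is date arithmetic.

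**Inputs.** Reporting period 30 days (3.8). Contact tolerance ± 7 days (1.4, 3.8, 4.3.2, footnote 19). Sunitinib off period 2 weeks (7.2.2). Dose holds that can end in permanent discontinuation: for savolitinib, 1 to 2 weeks for liver tests (6.8.1.2), more than 7 days for persistent Grade 3 toxicity (Table 9) and 21 days for QTcF (Table 10); for sunitinib, more than 7 days for persistent Grade 3 toxicity (Table 11).

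**Step 1, contact against duty, both counted from the same day.** Earliest contact 30 − 7 = day 23; latest 30 + 7 = day 37. Days left after the earliest contact: 30 − 23 = 7, and 7/30 = 23%.

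**Step 2, effect of the anchor.** Let g be the days from the last dose to the date taken as discontinuation, with the contact timed from discontinuation. In days after the last dose:
- window end, last-dose rule: 30
- window end, discontinuation rule: 30 + g
- contact: 23 + g to 37 + g
- days not covered by the earliest contact: max(0, 7 − g) under the last-dose rule, and always 7 under the discontinuation rule

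| g | Example | Window end: last-dose / discontinuation rule | Contact | Uncovered: last-dose / discontinuation rule |
|---|---|---|---|---|
| 0 | uninterrupted dosing, either arm | 30 / 30 | 23–37 | 7 / 7 |
| 7 | one-week hold | 30 / 37 | 30–44 | 0 / 7 |
| 14 | end of sunitinib off period, or two-week hold | 30 / 44 | 37–51 | 0 / 7 |
| 21 | QTcF hold to its limit | 30 / 51 | 44–58 | 0 / 7 |

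Subtracting cycle day 28 from day 43 gives 15 for the sunitinib off period; counting only off-drug days gives 14.

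**Step 3, which meaning of discontinuation?** The end-of-treatment visit is timed from the decision to stop (1.4, 3.8.1, 4.3.1), and 3.8.1 has a discontinuation date recorded. Reading it as the decision date is therefore reasonable. The blended phrase in 3.8 supports reading it as the last dose, and then g = 0. The text does not settle it.

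**Step 4, after the change.** With a last-dose anchor and contact on day 30 to 37, uncovered days are max(0, 30 − 30) = 0, and both arms have the same 30-day window.

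**The case against.** The ± 7 days is a visit tolerance and does not shorten the duty to report to day 30. AEs also reach the site through the eDiary, open questions and observation (6.3.5). Ongoing events are followed to resolution or stability, and possibly related later events remain reportable. All of this stands, and it limits the likely loss mainly to new, non-serious events in some patients. One backstop is weaker than it looks. The hospital-resource form prompts SAE entry, but Table 1 footnote 17 runs it only until the Safety Follow-up, so it too may end on day 23.

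A reader might infer that sunitinib patients have an AE window 14 days longer than savolitinib patients. The documents do not support that as a general statement:
- It requires discontinuation to mean the decision date.
- It requires stopping at the cycle-start scan. Section 1.4 says dosing should continue during central verification of progression unless medically contraindicated, and 5.1.3 says it may; turnaround is generally within 10 days. A patient who carries on into the next dosing block has a gap near zero. Stopping earlier is possible under 3.8.1.
- Savolitinib holds of one to three weeks before discontinuation create the same or a larger gap, so savolitinib is not fixed at 30 days.

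A reader might also add the two effects together. They do not add: where g is 7 or more, even the earliest contact covers 30 days from the last dose. Nor is the last-dose anchor an isolated slip, since 4.3.2 and 6.3.2 use its equivalent.

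Finally, a statistical analysis plan may fix the cut-off for AE tables. It cannot repair the timing of a site contact, and 8.4.2 already states an anchor that differs from 3.8.

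**Conclusion.** The point holds, with modest impact. Up to 7 of the 30 reportable days (23%) can fall after the only planned AE enquiry, and 4.3.5 lets the later SAE collection period itself end on day 23. The 23% is a share of calendar days, not of events; the protocol gives no event rate for this period.

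The anchors are inconsistent between and within sections. If discontinuation is the last dose, this changes nothing numerically. If it is the decision date, the window runs past day 30 by 0 to about 14 days for sunitinib stopped at the end of its off period, and by a similar or longer time in either arm after a hold. The size and direction of any difference between arms cannot be determined. Safety is summarised descriptively and not tested, so what is affected is the completeness and comparability of those summaries, not a formal inference.

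**What to change.** Define the 30-day AE window from the date of the last dose taken, and use that definition in 1.4, 3.8, 4.3.2, 4.3.5, 6.3.1, 6.3.2, Table 1 footnote 19 and the AE summary rule in 8.4.2. Hold the safety contact on day 30 to day 37 after the last dose and have it ask about the whole period. In 4.3.5, keep any tolerance on the contact and fix the collection period at 30 days.

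The cost is amendment wording, with no extra visit. The downside is that some contacts take place up to a week later than they otherwise would.

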3.9 Criteria for withdrawal from the study

Reasons for withdrawal from the study:

- Voluntary withdrawal by the patient who is at any time free to discontinue their participation in the study without prejudice to further treatment.
- Incorrectly enrolled patients ie, the patient does not meet the required inclusion/exclusion criteria for the study. This option is only applicable to patients not randomised into the study (ie, screen failures identified prior to randomisation).

If a patient voluntarily withdraws consent, they will fill out the Withdrawal ICF (Informed Consent Form Addendum – Options for Withdrawal of Consent) and be specifically asked if they are withdrawing consent for further follow-up, eg, survival calls.

3.9.1 Screen failures

Screen failures are patients who either are not MET-driven (Part 1 screen failures), and therefore cannot go on to the main study (Part 2) screening, or who do not fulfil the eligibility criteria for the main study (Part 2 screen failures), and therefore must not be randomised. These patients should have the reason for study withdrawal recorded as “Screen failure” (ie, the potential patient does not meet one or more of the required inclusion/exclusion criteria) in IVRS/IWRS). ‘Failure to meet randomisation criteria’ should be selected for situations where the patient has been unable to fulfil/satisfy the main study (Part 2) criteria required for assignment into a randomised group.

3.9.2 Withdrawal of the informed consent

Patients are at any time free to withdraw from the study (study medication and assessments), without prejudice to further treatment. Such patients will always be asked about the reason(s) and the presence of any AEs. If possible, they will be seen and assessed by an investigator. Adverse events will be followed up (see Sections 6.3.2 and Section 4.3.2). All study medication and empty study medication bottles should be returned by the patient as well as the electronic PRO (ePRO) devices.

If a patient withdraws from the study, then his/her enrolment/randomisation code cannot be reused.

In the event that the patient has actively withdrawn consent to the processing of their personal data, the vital status of the patient can be obtained by site personnel from publicly available resources where it is possible to do so under applicable local laws.

3.10 Discontinuation of the study

The study may be stopped if, in the judgment of AstraZeneca, trial subjects are placed at undue risk because of clinically significant findings that:

- meet individual stopping criteria or are otherwise considered significant.
- are assessed as causally related to study medication.
- are not considered to be consistent with continuation of the study.

Regardless of the reason for termination, all data available for the patient at the time of discontinuation of follow-up must be recorded in the eCRF. All reasons for discontinuation of treatment must be documented.

In terminating the study, the Sponsor will ensure that adequate consideration is given to the protection of the patients' interests.

4. STUDY PLAN AND TIMING OF PROCEDURES

Table 1 Study schedule: Screening, On Study Treatment, Discontinuation and Follow-up

	Part 1 Screening Visit	Part 2 Screening Visit ²	Cycle 1						Cycle 2						Cycle 3 & beyond (every 6 weeks)	EOT ¹⁸	Safety Follow-up ¹⁹	PFS ²²	Overall Survival Follow-Up ²⁰
			D 1	D 8	D 15	D 22	D 29	D 36	D 1	D 8	D 15	D 22	D 29	D 36	D1				
Site Visit	0	1	2	3	4	5	6	7											
Day		-28 to 0	1	8	15	22	29	36	43	50	57	64	71	78	85				
Activity Visit Window			0	± 2d	± 2d	± 2d	± 2d	± 2d	± 2d	± 2d	± 2d	± 2d	± 2d	± 2d	± 7d				
Part 1 Screening Informed Consent Form ¹	X																		
Demography, medical/surgical history ³	X																		
Cancer therapy ⁴	X															X	X	X	X
FFPE tumour sample for MET-driven status ⁶	X																		
██████████ ██████████ ██████████ ██████████	X																		
Main Study (Part 2) Informed Consent Form ¹		X																	
Physical examination		X	X	X	X	X	X	X	X	X	X	X	X	X	X	X*	X ²⁷		
Body weight ²⁵		X	X					X						X					
Vital signs ⁵		X	X	X	X	X	X	X	X	X	X	X	X	X	X	X*	X ²⁷		

Table 1 Study schedule: Screening, On Study Treatment, Discontinuation and Follow-up

	Part 1 Screening Visit	Part 2 Screening Visit ²	Cycle 1						Cycle 2						Cycle 3 & beyond (every 6 weeks)	EOT ¹⁸	Safety Follow- up ¹⁹	PFS ²³	Overall Survival Follow- Up ²⁰
			D 1	D 8	D 15	D 22	D 29	D 36	D 1	D 8	D 15	D 22	D 29	D 36	D1				
Site Visit	0	1	2	3	4	5	6	7											
Day		-28 to 0	1	8	15	22	29	36	43	50	57	64	71	78	85				
Activity Visit Window			0	± 2d	± 2d	± 2d	± 2d	± 2d	± 2d	± 2d	± 2d	± 2d	± 2d	± 2d	± 7d				
Tumour Assessment ¹⁶		X						X							X			X (by institutional call)	
Karnofsky Performance Status		X	X					X							X	X*			
Smoking Status (Y/N) ²⁴		X																	
Haematology		X	X	X	X	X	X	X	X	X					X	X*	X ²⁷		
Clinical Chemistries ²⁹		X	X	X	X	X	X	X	X	X					X	X*	X ²⁷		
Corrected calcium ³¹		X																	
Liver function tests ²¹		X	X	X	X	X	X	X	X	X					X	X*	X ²⁷		
Hepatitis serology ³⁰		X																	
Coagulation ⁷		X ⁷																	
Urinalysis ⁸		X		X	X	X	X	X	X	X					X		X ²⁷		

Table 1 Study schedule: Screening, On Study Treatment, Discontinuation and Follow-up

	Part 1 Screening Visit	Part 2 Screening Visit ²	Cycle 1						Cycle 2						Cycle 3 & beyond (every 6 weeks)	EOT ¹⁸	Safety Follow-up ¹⁹	PFS ²³²	Overall Survival Follow-Up ²⁰
			D 1	D 8	D 15	D 22	D 29	D 36	D 1	D 8	D 15	D 22	D 29	D 36	D1				
Site Visit	0	1	2	3	4	5	6	7											
Day		-28 to 0	1	8	15	22	29	36	43	50	57	64	71	78	85				
Activity Visit Window			0	± 2d	± 2d	± 2d	± 2d	± 2d	± 2d	± 2d	± 2d	± 2d	± 2d	± 2d	± 7d				
Thyroid Function tests, LDH		X						X							X				
Pregnancy test ⁹		X	X					X							X	X			
Triplicate ECGs ¹⁰		X	X	X	X	X	X	X							X	X			
Echocardiogram/MUGA ¹⁰		X	Every 12 weeks (±2 weeks) relative to first dose 												X				
Prophylactic dental exam ¹²		X																	
Pharmacogenetic sample ¹¹			X																
PK blood collection ¹³			X	X	X				X										
██████████ ██████████ ██████████		X	X					X							X	X			
██████████ ██████████ ██████████		X	X					X								X			

Table 1 Study schedule: Screening, On Study Treatment, Discontinuation and Follow-up

	Part 1 Screening Visit	Part 2 Screening Visit ²	Cycle 1						Cycle 2						Cycle 3 & beyond (every 6 weeks)	EOT ¹⁸	Safety Follow-up ¹⁹	PFS ²³	Overall Survival Follow-Up ²⁰
			D 1	D 8	D 15	D 22	D 29	D 36	D 1	D 8	D 15	D 22	D 29	D 36	D1				
Site Visit	0	1	2	3	4	5	6	7											
Day		-28 to 0	1	8	15	22	29	36	43	50	57	64	71	78	85				
Activity Visit Window			0	± 2d	± 2d	± 2d	± 2d	± 2d	± 2d	± 2d	± 2d	± 2d	± 2d	± 2d	± 7d				
FACIT-F and PRO CTCAE ¹⁷			X	Bi-Weekly for the first 18 weeks relative to the first dose, then every 4 weeks until EOT visit											X				
EQ-5D-5L and FKSI-19 ¹⁷			X	Every 4 weeks until EOT visit											X				
Hospital Resource Use ¹⁷			X		X		X							X		X			
Concomitant Medications		X	X	X	X	X	X							X	X				
Adverse Events ²³		X	← continuously →												X				
Drug Dispensing/Return ³³			X					X						X	X (return only)				
IVRS/IWRS transactions ²²	X	X	X					X						X	X				
Tumour biopsy at relapse ²⁸															X				

- 1 Written informed consent must be obtained before any Part 1 or Part 2 screening activities occur.
- 2 Part 2 screening assessments must take place within 28 days of signing the ICF for Part 2. Assessments obtained outside of the 28-day window must be repeated before Cycle 1 Day 1.
- 3 Demographic information (age, sex, race, and ethnicity) and a complete medical and surgical history on all (both MET-driven and MET-negative) patients will be collected and recorded in the appropriate eCRFs at the Part 1 screening visit. The medical history will include smoking history in pack years
- 4 All previous cancer treatments, including line of therapy, dates of administration, and best response to treatment on all (both MET-driven and MET-negative) patients will be collected and recorded in the appropriate eCRF at the Part 1 screening visit. During follow-up, cancer treatments administered since discontinuing study treatment will be collected.
- 5 Vital signs include: heart rate, systolic and diastolic blood pressure, height [only at the main study screening] and temperature.
- 6 FFPE tumour sample(s) that meet the specifications in the Laboratory Manual will be analysed prospectively by the sponsor-designated central laboratory by NGS for MET-driven status prospectively, or after study entry in cases where a pre-existing “MET-driven” result is available. See Section 1.4 for qualifying MET-driven alterations.
- 7 If INR and aPTT are normal at baseline, they do not need to be repeated unless clinically indicated during the study. Patients on anti-coagulant therapy should have coagulation testing performed according to standard management guidelines.
- 8 Urinalysis: If 3+ or greater proteinuria is identified by dipstick assessment, a 24-hour urine collection for formal quantification of the level of protein excretion should be performed.
- 9 Women of childbearing potential will have a serum or urine pregnancy test done at main study screening pre-dose Cycle 1 Day 1, on Day 1 of each subsequent cycle, and at treatment discontinuation.
- 10 Triplicate ECGs will be performed during the main study (Part 2) screening period, every week in the first cycle, every cycle thereafter, at the end of treatment visit if not done within the last 6 weeks, and at other times if clinically indicated. Echocardiogram/MUGAs will be performed during the main study (Part 2) screening period, every 12 weeks (± 2 weeks) relative to the first dose of study medication, at the end of treatment visit if not done within the last 6 weeks, and at other times if clinically indicated.
- 11 A 10-mL blood sample for [REDACTED] will be obtained from the patient pre-dose on 1 Day 1 ([REDACTED]). If for any reason the sample is not drawn prior to dosing it may be collected as soon as possible thereafter. Only one sample will be collected. See Section 5.6.
- 12 Patients who have ever received bisphosphonates should undergo a maxillofacial exam during the main study (Part 2) screening period with treatment of active infection and prophylactic treatment of any sites that are at high risk for infection.
- 13 Blood sample (2 mL) to be collected from patients assigned to savolitinib pre-dose on Day 1 of Cycle 1, pre-dose and 1 and 3 hours post dosing on Day 15 of Cycle 1, and pre-dose on Day 29 of Cycle 1 and on Day 57 (ie, Day 15 of Cycle 2). The date/time of the last two doses prior to the pre-dose PK samples (should be confirmed in the patient diary) and the date/time the PK sample was drawn and the dose/time the savolitinib is given on the PK day need to be recorded in the eCRF.
- 14 [REDACTED] (10 mL whole blood) will be collected at the Part 2 screening visit and pre-dose Cycle 1 Day 1, and on the same day as each tumour evaluation (including unscheduled evaluations), corresponding to at least every 6 weeks during the first year and 12 weeks thereafter, and at EOT, regardless of whether a sample was just collected at the last scan (see Section 5.7.5).
- 15 A [REDACTED] (10 mL whole blood) will be collected at the Part 2 screening visit, pre-dose Day 1, Cycle 1, at the time of the first tumour evaluation (Cycle 2, Day 1) and at EOT (please see Section 5.7.6).

- 16 Baseline tumour imaging studies will be performed within 28 days prior to the date of randomisation and will be repeated every 6 weeks (± 1 week),
corresponding to the start of each cycle during the first year and then every 12 weeks (± 1 week) thereafter, until BICR-confirmed PD using RECIST 1.1.
- 17 All PRO (FACIT-F, FKSI-19, PROCTCAE and EQ-5D-5L) questionnaires should be completed using the e-PRO device on the schedule above. The site
should check the PRO data and patient compliance on the web-based portal at every clinic visit. All four questionnaires need to be completed at the EOT
visit prior to the patient meeting with the physician and then the e-PRO devices should be collected. See section 5.3.2 for hospital resource use, which
should be completed using the HOSPAD module on a continuous basis until the Safety Follow-up.
- 18 See Section 4.3.1. The asterisked assessments* do not need to be repeated if done within the last 2 weeks and there is no need for follow-up of toxicity. An
ECHO/triplicate ECGs need to be performed if not done within the last 6 weeks. [REDACTED] and a pregnancy test need to
be performed. The ePRO device and all unused study medication and study medication bottles should be returned.
- 19 A safety follow-up will be performed 30 (± 7) days after discontinuation of study medication, to follow-up on any SAE/AE's and record any subsequent
cancer therapy. If there are no ongoing SAE/AEs at the time of drug discontinuation, the safety follow-up can be done via telephone contact.
- 20 All subsequent anti-cancer therapies and OS status will be documented at least every 12 weeks until death, loss to follow-up, withdrawal of consent, or end
of study, whichever comes first.
- 21 Blood liver functions (AST, ALT, alkaline phosphatase and total bilirubin) will be monitored weekly x 9 and then at the start of each cycle. In some
situations, blood for LFTs may be drawn at a local lab on the days when there is no scheduled clinic visit although the results must be faxed to the treating
institution immediately so they can be evaluated in light of the hepatotoxicity algorithm (Section 6.8.1.2 for savolitinib and Section 6.8.2 for sunitinib) and
entered into the database.
- 22 An IVRS/IWRS transaction needs to be done at every dispensing visit at the start of each cycle. Additionally, every dose reduction needs to be recorded in
IVRS/IWRS.
- 23 Please see section 6.3. From the part 1 screening visit until the part 2 screening visit, only SAEs related to study procedures must be reported (AEs do not
require reporting). From the main study screening (Part 2) onwards, all AEs/SAEs must be reported
- 24 Smoking status (Yes (current smoker) /No (not currently smoking)) will be recorded at the time of the main study screening (Part 2) visit.
- 25 Body weight will be assessed every cycle, and more frequently if clinically indicated. The dose of savolitinib will not change for patients who started the
study at < 50 kg (ie, 400 mg), even if their weight increases to ≥ 50 kg during the course of the study.
- 26 20 mL for [REDACTED] at the Part 1 screening visit only (see Section 5.7.4)
- 27 Only necessary if there are ongoing toxicities
- 28 A tumour biopsy after treatment discontinuation should be strongly encouraged regardless of treatment arm, particularly for patients who had responded to
treatment. See section 5.7.7.
- 29 See Table 2 (Section 5.2.1) for list of chemistry evaluations
- 30 Hepatitis serology includes HBsAg, anti-HBc (qualitative), HBV DNA, HCV antibody, HCV RNA (if HCV antibody is positive)
- 31 To be used for determination of IMDC risk category. Corrected calcium = total calcium (mg/dL) $- 0.707$ [albumin (g/dL) $- 3.4$]
- 32 Patients will enter the PFS2 follow-up period once the patient has discontinued study medication due to PD by RECIST 1.1. Patients will be followed at
least every 12 weeks by site personnel for second progression on subsequent anti-cancer therapy and documentation of all subsequent therapy.

- ³³ The number of remaining pills at the end of each cycle should be recorded in RAVE. Additionally, patients must bring their medication bottles or blister packs and all remaining tablets or capsules to each clinic visit so that a medication count and reconciliation can be done in conjunction with the medication diary as well as to ensure that the patient has sufficient medication remaining until the next visit. The results of the medication counts and reconciliation should be recorded on IP Accountability logs.

